13.1.5. Additional Investigator Responsibilities for SAEs

The safety data recorded in the EDC represent the official record of all AEs and SAEs reported in the study. The Investigator should comply with requests by the Medical Monitor or other Sponsor personnel to record the SAE on the patient's AE EDC. Other supporting documents such as radiology reports, hospital discharge summaries, and autopsy reports should also be provided, when appropriate. Additionally, upon request by the Sponsor, the Investigator should provide input into the SAE narrative and provide timely information to ensure prompt follow-up and closure of the SAE report.

The Investigator and supporting personnel responsible for patient care should discuss with the Medical Monitor any need for supplemental investigations of SAEs. The results of these additional assessments must be reported to the Medical Monitor.

13.1.6. Notification of Post-Treatment SAEs for Patients Who Continue in the Study

Post-treatment SAEs that occur in patients who remain in the study after investigational product has been discontinued must be reported to the Sponsor within 24 hours by following the instructions provided in [Section 13.1.4.2](#).

SAEs that occur in patients who discontinue investigational product, initiate treatment with commercially available Ocaliva, and remain in the study must be reported to the Sponsor within 24 hours by following the instructions provided in [Section 13.1.4.2](#).

13.1.7. Notification of Post-Study SAEs

All SAEs that occur within 30 days following discontinuation from the study, whether or not they are related to the investigational product, must be reported to the Sponsor within 24 hours by following the instructions provided in [Section 13.1.4.2](#).

If an Investigator becomes aware of an SAE that may be attributable to the investigational product at any time after the end of the study, the Sponsor should be notified immediately (ie, within 24 hours) by following the instructions provided in [Section 13.1.4.2](#).

13.1.8. Follow-Up of AEs and SAEs

All AEs must be followed during the course of the study until the AE resolves, is no longer of clinical concern, has stabilized or is otherwise explained, or the patient is lost to follow-up.

AEs ongoing at the final visit that are deemed to be “possibly, probably, or definitely” related or of other clinical significance must be followed for as long as necessary to adequately evaluate the safety of the patient or until the event stabilizes, resolves, or is no longer of clinical concern. If resolved, a resolution date for the AE should be documented on the eCRF. The Investigator must ensure that follow-up includes any supplemental investigations indicated to elucidate the nature and/or causality of the AE. This may include additional laboratory tests or investigations, or consultation with other healthcare professionals, as considered clinically appropriate by the Investigator.

All patients showing possible drug-induced liver injury should be followed until all abnormalities return to normal or to the baseline state. Drug-induced liver injury may develop or progress even after the causative drug has been stopped. Results should be recorded in the eCRF. Note that longer follow-up can sometimes reveal an off-drug repetition of what had appeared to be drug-induced liver injury, indicating that liver injury was related to underlying liver disease.

13.1.9. Pregnancy and Follow-Up

Pregnancies are not considered AEs in and of themselves; however, if a female study participant becomes pregnant while she is enrolled in the clinical study, she must interrupt treatment with investigational product immediately (see [Section 8.4.1.3](#)) and the Sponsor must be notified within 24 hours of the Investigator’s awareness of the pregnancy by completing the Pregnancy CRF in the EDC system and downloading and completing the Pregnancy Report Form. The Pregnancy Report Form must be emailed to PPD [REDACTED] or faxed to PPD [REDACTED]. The patient and neonate must be followed for outcome information and/or as considered appropriate by the Investigator and Sponsor.

The patient may restart investigational product when she is no longer pregnant or breastfeeding (if applicable) at the discretion of the Investigator and after discussion with the Medical Monitor. The patient must have a negative pregnancy test before restarting investigational product. If a patient’s pregnancy is terminated early (planned or unplanned), she must have termination of the pregnancy confirmed by a serum β -hCG test before restarting investigational product.

Completing the Pregnancy Report Form is not a substitute for reporting an AE/SAE when and AE/SAE has occurred. In the situation when an AE/SAE has occurred, the AE/SAE reporting procedures described in [Section 13.1.4](#) must also be followed.

13.2. Other Safety Parameters

13.2.1. Medical History/Demographics

A complete medical history will be obtained from the patient at screening. Demographic characteristics (age, gender, race, and ethnicity) will be recorded.

13.2.2. Physical Examination

To assess for clinical findings, the Investigator or designee will perform a physical examination at the visits specified in the Schedule of Study Procedures (Table 1). A basic physical examination should be performed, including all body systems pertinent to the patient. Smoking and alcohol consumption history and current habits will be recorded. Any clinically significant abnormality should be reported on the AE eCRF page for findings that appear after consent, and on the medical history eCRF for any finding present prior to consent.

13.2.3. Vital Signs and Weight

Vital signs (oral temperature, sitting heart rate, respiratory rate and sitting blood pressure [BP]) and weight will be assessed at indicated visits (Table 1). When taking heart rate, respiratory rate and BP readings, patients should be seated quietly for a minimum of 3 minutes before the readings are taken.

13.2.4. Electrocardiogram

Standard ECGs will be collected. The Investigator or designee will review the ECG and findings will be recorded in the eCRF as normal, abnormal but not clinically significant, or abnormal and clinically significant. Any clinically significant abnormalities on ECGs recorded after Day 1 will also be documented as AEs and entered on the AE page of the eCRF.

Investigative sites must retain a copy of all ECGs evaluated by the Investigator or designee. These ECGs must be clearly labeled with the Patient ID number, date, and time. Full instructions will be provided for forwarding the ECGs for central reading.

13.2.5. Laboratory Assessments

Except for Screening, patients will be instructed to attend each study visit in a fasted state, preferably in the morning, and patients should remain fasted until their blood samples have been collected. At all visits (except screening), the Investigator or designee will verify that the patient has fasted for at least 8 hours and record fasting status in the source and eCRF. If the patient reports having eaten (water is permitted) within 8 hours, the Investigator or designee will document accordingly in the source and eCRF and remind the patient that fasting is required before all study visits.

Blood samples for serum chemistry, coagulation, and hematology; and urine samples will be collected at visits as detailed in the Schedule of Study Procedures (see Table 1). The number and volume of samples to be collected at each visit will be detailed in the laboratory manual.

Full instructions concerning the number and type of samples to be collected at each visit, the required sample volumes, sample collection methods, sample processing, labeling, and shipping will be provided in a separate procedural manual. All necessary collection supplies will be provided by the central laboratory and will be appropriately assembled for the specific evaluations required at each visit.

All patients with laboratory tests containing clinically significant abnormal values are to be followed regularly until the values return to normal ranges; until a valid reason, other than investigational product related AE, is identified; or until further follow-up is deemed medically unnecessary.

Laboratory samples will be stored for a maximum of up to 1 year after the end of the study (depending on stability) in the event that retesting is required, and destroyed after 1 year if not analyzed.

The list of laboratory analytes to be tested is shown in Table 9.

Table 9: List of Laboratory Analytes to be Tested

Laboratory Assessment	Analyte
Serum Chemistry	Albumin, blood urea nitrogen, creatinine, direct bilirubin, total bilirubin, aspartate aminotransferase [AST, SGOT], alanine aminotransferase [ALT, SGPT], ALP, GGT, electrolytes [calcium, chloride, potassium, sodium], glucose, total protein, and blood lipids (total cholesterol, LDL, HDL and VLDL fractions and TG), CPK, magnesium, phosphorus, bicarbonate, unconjugated (indirect) bilirubin, conjugated (direct) bilirubin, free fatty acids, TFT (TSH, free T3 and free T4)
Hematology	Hemoglobin, hematocrit, white blood count with differential, neutrophils, lymphocytes, monocytes, eosinophils, basophils, platelets, red blood cell count (including MCV, MCH, MCHC)
Coagulation	PT, PTT, INR
Urinalysis (dipstick)	pH, specific gravity, total protein, glucose, ketones, bilirubin, blood, microscopic exam, urobilinogen, albumin, creatine, leucocytes, nitrates, albumin/creatinine ratio (if positive), pregnancy
Markers of Inflammation	IL-6, hs-CRP, TNF- α , IgM, IgA, IgG, CK-18-M30
Noninvasive measurements of liver fibrosis, liver stiffness and cirrhosis	ELF (HA, P3NP, and TIMP-1) TE
PK assessments	OCA (parent and conjugates [glyco and tauro], metabolite OCA-glucuronide)
PD markers	C4, FGF-19 and plasma bile acids

ALP = alkaline phosphatase; ALT = alanine aminotransferase; AST = aspartate aminotransferase; C4 = 7 α -hydroxy-4-cholesten-3-one; CK-18-M30 = cytokeratin-18 neopeptide M30; CP = Child-Pugh; CPK = creatine phosphokinase; ECG = electrocardiogram; ELF = enhanced liver fibrosis; FGF-19 = fibroblast growth factor-19; GGT = gamma-glutamyl transferase; HA = hyaluronic acid; HDL = high density lipoprotein; hs-CRP = high-sensitivity C-reactive protein; IgA = immunoglobulin A; IgG = immunoglobulin G; IgM = immunoglobulin M; IL-6 = Interleukin 6; INR = international normalized ratio; LGL = low-density lipoprotein; MCH = mean corpuscular hemoglobin; MCHC = mean corpuscular hemoglobin concentration; MCV = mean corpuscular volume; OCA = obeticholic acid; PBC = primary biliary cirrhosis; P3NP = procollagen 3 N-terminal peptide; PT = Prothrombin time; PTT = partial thromboplastin time; SGOT = Serum glutamic oxaloacetic transaminase; SGPT = serum glutamic-pyruvic transaminase; TE = Transient Elastography; TG = triglyceride; TFT = thyroid function test; TIMP-1 = tissue inhibitor of metalloproteinase 1; TNF- α = tumor necrosis factor- α ; VLDL = very-low density lipoprotein

Laboratory reference ranges for the study will be based on the laboratory vendor range.

Urine based β -hCG pregnancy tests will be performed in female patients of childbearing potential per protocol specified visits (see [Table 1](#)). If a urine pregnancy test is positive, a serum pregnancy test must be performed to confirm the result. If positive, the Sponsor must be notified and the patient will be followed as outlined in [Section 13.1.9](#) until pregnancy outcome.

INR will be calculated based on prothrombin time value by the central laboratory. MELD scores will be calculated based on creatinine, bilirubin, Na, and INR values, with modification by

United Network for Organ Sharing. Total OCA will be calculated based on OCA, tauro-OCA, glyco-OCA, and metabolite OCA glucuronide concentrations. Laboratory analyte results may be used to calculate various cardiovascular risk and fibrosis measurement scores.

13.2.6. Patient-Reported Outcomes and Healthcare Resource Use

Data will be collected to determine the effects of OCA on health-related quality of life. Healthcare resource use as well as a general health status assessment (for the purposes of generating health utilities) will be used to support subsequent cost-effectiveness analyses that are relevant to major health care systems around the world. Assessments of patient-reported outcomes will take place during the visits indicated in [Table 1](#).

The following patient-reported outcomes will be used to evaluate the effects of OCA compared to placebo on improvements in health-related quality of life:

- PBC-40: The PBC-40 is a validated disease-specific 40-question quality of life questionnaire, which consists of 6 domains: General Symptoms, Itch, Fatigue, Cognitive Function, Social, and Emotional ([Jacoby 2005](#)).
- EQ-5D-5L: The EQ-5D-5L consists of 2 sections – the descriptive system and the visual analogue scales (VASs). The descriptive system is organized into 5 dimensions: mobility, self-care, usual activities, pain/discomfort, and anxiety/depression. Each dimension has 5 levels: no problems, slight problems, moderate problems, severe problems, and extreme problems. The VAS records the patient’s self-rated health on a 20-cm vertical, line with endpoints labelled “the best health you can imagine” and “the worst health you can imagine” ([Herdman 2011](#), [Oemar 2013](#)).
- Pruritus VAS: A VAS will also be used to assess pruritus in individual patients.
- CLDQ: The CLDQ is a disease-specific health related quality of life questionnaire for patients with chronic liver disease. The questionnaire includes 29 items in the following domains: fatigue, activity, emotional function, abdominal symptoms, systemic symptoms, and worry). Each question is answered on a scale from 1 (always) to 7 (never) with a higher score corresponding to a better quality of life. The CLDQ produces a summary score and domain scores that correlate with the severity of liver disease ([Younossi 1999](#)).

Patients will be asked to complete the questionnaires and initial and date each document. The questionnaires should be filed in the patient’s study records. These may require transcription to the eCRF by study site staff.

Healthcare resource use will be collected from eCRFs including number, reason for and duration of hospitalizations and emergency room visits, number of outpatient physician visits (patient reported), and use of concomitant medications. The purpose is to evaluate the effects of OCA compared to placebo on patient-reported outcomes and healthcare resource.

14. EFFICACY ASSESSMENTS

14.1. Biochemical Measures of Disease Severity

14.1.1. Child-Pugh Score

Child-Pugh Score (Pugh 1973, Lucey 1997) is calculated and reported within the EDC system based on data entered into the eCRF by adding the scores from the 5 factors outlined in Table 10 and can range from 5-15. A total score of 5-6 is considered Grade A (mild, well-compensated disease); 7-9 is Grade B (moderate, significant functional compromise); and 10 and above is Grade C (severe, decompensated disease). Calculation of the CP Score includes Investigator assessments of ascites and hepatic encephalopathy, which may be assessed during the adverse event review at the scheduled visits, as well as total bilirubin, serum albumin, and prothrombin time, which will populate from the central laboratory. Investigators will be responsible for determining the appropriate dosing regimen based on the CP score (Table 1 and Table 10). Any change in CP Score will necessitate re-evaluation of the dosing regimen.

Table 10: Child-Pugh Scoring System

Factor	Units	Points		
		1	2	3
Serum bilirubin	mg/dL	<2.0	2.0-3.0	>3.0
Serum albumin	g/dL	>3.5	2.8-3.5	<2.8
Prothrombin time	Seconds prolonged	0-3	4-6	>6
	INR	<1.7	1.7-2.3	>2.3
Ascites		None	Mild	Moderate-Severe
Hepatic encephalopathy ^a		0	Grade 1 or 2	Grade 3 or 4

^a Grade 0: normal consciousness, personality, neurological examination, electroencephalogram
 Grade 1: restless, sleep disturbed, irritable/agitated, tremor, impaired handwriting, 5 cps waves
 Grade 2: lethargic, time-disoriented, inappropriate, asterixis, ataxia, slow triphasic waves
 Grade 3: somnolent, stuporous, place-disoriented, hyperactive reflexes, rigidity, slower waves
 Grade 4: unrousable coma, no personality/behavior, decerebrate, slow 2-3 cps delta activity
 (Pugh 1973, Lucey 1997)

14.1.2. Model of End Stage Liver Disease Score

The MELD scoring system is used to assess the severity of chronic liver disease. The MELD score is useful in assessing patients with significant decompensation, and the MELD score is now used by the United Network for Organ Sharing in the US and Eurotransplants to manage the organ allocation for liver transplantation. The threshold for placement on an organ transplantation queue varies between regions across the globe.

An increasing MELD score is associated with increased severity of hepatic dysfunction and increased 3-month mortality risk. The MELD score is derived from the patient's serum total

bilirubin, serum creatinine, and INR, as appropriate, to predict survival and is calculated according to the following formula ([Kamath 2007](#)):

$$\text{MELD} = 3.78 \times \ln[\text{serum bilirubin (mg/dL)}] + 11.2 \times \ln[\text{INR}] + 9.57 \times \ln[\text{serum creatinine (mg/dL)}] + 6.43$$

MELD score will be calculated and reported in whole numbers according to the frequency listed in [Table 1](#).

14.1.3. Changes in Liver Biochemistry and Hepatobiliary Damage

ALP, ALT, AST, GGT, total and direct bilirubin, INR, creatinine, albumin, platelets will be measured according to the frequency listed in [Table 1](#).

14.2. Additional Assessments

14.2.1. Markers of Inflammation, Apoptosis and Necrosis

Blood samples for analytes including IL-6, hs-CRP, IgA, IgG, IgM, TNF- α , cytokeratin-18 neopeptide M30. Assessments will be performed according to the schedules presented in [Table 1](#).

14.2.2. Noninvasive Measurements of Liver Stiffness and Fibrosis

The ELF test assesses: HA, P3NP, and TIMP-1. Samples will be assessed in patients according to the schedules presented in [Table 1](#).

The Fibroscan® TE device (Echosens, Paris, France) will be used at all study sites that have the equipment to collect hepatic stiffness measurements. These study sites must have the staff trained in the use and data interpretation of the device. This is a validated and non-invasive technique used to assess hepatic fibrosis which will be conducted according to the schedule presented in [Table 1](#).

14.2.3. Markers of FXR activation

Blood samples will be collected in all patients to measure C4, FGF-19, and bile acids. The results of these analyses will be used to assess the PK/PD response of OCA. Blood samples will be assessed in patients according to the schedule presented in see [Table 1](#).

14.2.4. Clinical Outcome Events

Clinical outcome events will be evaluated by an Adjudication Committee (described in [Section 15.9](#)) to confirm if they meet the criteria to be considered Clinical Outcome Events.

15. STATISTICAL METHODS AND ANALYSES

Individual patient data obtained from electronic case report forms (eCRFs), central laboratories, external sources, and any derived data will be presented in data listings by patient. All data listings that contain an evaluation date will contain a relative study day. Pre-treatment and on treatment study days are numbered relative to the day of the first dose of investigational product which is designated as Day 1.

All output will be incorporated into Microsoft Word rich text format (.rtf) files, sorted and labeled according to the ICH recommendations, and formatted to the appropriate page size(s).

Tabulations will be produced for appropriate demographic, Baseline, efficacy, and safety parameters.

For categorical variables, summary tabulations of the number and percentage of patients within each category (with a category for missing data) of the parameter will be presented. Percentage calculations will be based on non-missing data, unless otherwise specified. Percentages are rounded to 1 decimal place, unless otherwise specified.

For continuous variables, the number of patients, mean, standard deviation (SD), standard error of the mean (SEM), median, minimum, and maximum values will be presented. The precision of summary statistics, unless otherwise specified will be as follows: mean and median to 1 more decimal place than the raw data, and SD and SEM to 2 decimal places more than the raw data. In general, the decimal places should not exceed 3 decimal places unless appropriate. Confidence intervals (CIs) will be provided and will be rounded to 1 decimal place, unless otherwise specified.

Time-to-event data will be summarized using Kaplan-Meier (KM) methodology using 25th, 50th (median), and 75th percentiles with associated 2-sided 95% CIs, as well as percentage of censored observations.

There will be no formal hypothesis testing in this study. However, summary statistics for each treatment group will be presented, as well as 95% CIs for the difference between the treatment groups.

15.1. Analysis Populations

The following patient populations will be evaluated and used for presentation and analysis of the data:

- The Intent-to-Treat (ITT) Population will include all randomized patients who receive any amount of investigational product (OCA or placebo). The ITT Population will be the primary population used for summarizing efficacy assessments.
- The Safety Population will include all patients who received at least one dose of investigational product (placebo or OCA). The Safety Population will be the primary population used for safety analyses.
- The PK population will include all patients receiving OCA who have adequate concentration-time profiles to characterize OCA and its conjugates and must not have any major protocol deviations that potentially affect exposure levels.

15.2. Determination of Sample Size

To reasonably characterize the PK of OCA in patients with hepatic impairment, a simulation-based approach estimated a requirement of approximately 20 patients in the OCA treatment group assuming a 15% discontinuation rate. Ten patients on placebo will be included as a comparator. An additional 20 patients will be enrolled to support safety and efficacy

evaluations. Therefore, approximately 50 patients (including at least 20% of patients with CP-C) will be randomized.

15.3. Pharmacokinetic Analyses

The PK Population will be used for analysis of PK parameters, which include plasma OCA (parent) and its conjugates (glyco-OCA and tauro-OCA), total OCA, metabolite OCA glucuronide, and potentially other conjugates or metabolites not yet identified.

PK analysis will be based on the PK population. Values will be calculated using non-compartmental methods. The values will be summarized by active treatment group using descriptive statistics.

15.4. Safety Analyses

Safety analyses will be conducted using the Safety population. Safety data, including AEs, vital signs, ECG, and clinical laboratory results will be summarized by treatment group using the Safety Population.

The incidence of TEAEs and SAEs will be tabulated by system organ class (SOC) and preferred term for each treatment group, and similarly by severity and relationship to treatment.

Laboratory parameters, physical examinations including vital signs, and ECGs will be summarized by treatment group using descriptive statistics at Baseline and at each scheduled post-Baseline visit. The absolute change from baseline will also be summarized.

CP scores will be summarized by treatment group at Baseline and at each post-Baseline visit.

No inferential comparison with formal statistical hypothesis testing will be performed for safety endpoints.

15.4.1. Adverse Events

AEs will be coded using MedDRA. Summary tables of TEAEs will be provided.

Each AE summary will be displayed by treatment group. Summaries that are displayed by SOC and PT will be ordered by descending order of incidence of system organ class and preferred term within each system organ class. Summaries of the following types will be presented:

- Overall summary of TEAEs.
- Patient incidence of TEAEs and the total number of entries by MedDRA SOC and PT. This summary will be repeated for all subgroups.
- Patient incidence of TEAEs by MedDRA SOC, PT, and highest severity. At each level of patient summarization, a patient is classified according to the highest severity if the patient reported 1 or more events. AEs with missing severity will be considered severe for this summary.
- Patient incidence of TEAEs by MedDRA SOC, PT, and closest relationship to investigational product (Related/Not Related). Related AEs are those with relationships reported as “Definite,” “Probable,” or “Possible,” and unrelated AEs are those with relationships reported as “Unlikely” or “Not Related.” At each level of

patient summarization, a patient is classified according to the closest relationship if the patient reported 1 or more events. AEs with a missing relationship will be considered related for this summary.

- Patient incidence of serious TEAEs and the total number of entries by MedDRA SOC and PT.
- Patient incidence of TEAEs leading to investigational product withdrawal or study discontinuation by MedDRA SOC and PT. This is a subset of the AEs where Action Taken with Study Treatment is checked as “Drug Withdrawn” or where “Patient Discontinued from Study” is checked.

The following listings will be presented by treatment group and patient:

- All adverse events.
- Serious adverse events (This is a subset of the AEs where serious is marked as “Yes”).
- Severe adverse events (This is a subset of AEs where severity is marked as “Severe”).
- Related adverse events (This is a subset of the AEs where relationship marked as “Definite,” “Probable,” or “Possible”).
- Adverse events leading to Study Drug Withdrawal or Study Discontinuation (This is a subset of the AEs where Action Taken with Study Treatment is checked as “Drug Withdrawn” or where “Patient Discontinued from Study” is checked).
- Adverse events leading to death (This is a subset of the AEs where the corresponding AE number is specified on the Death eCRF).

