7.1.3. Study Duration

Patients will receive double-blind treatment for at least 48 weeks. Patients who have completed their 48-week double blind treatment period will continue double-blind treatment until all randomized patients have completed their 48-week treatment period and the database for that period is locked (approximately 3 years). Patients will then be given the option to go on open-label treatment.

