9. TREATMENT OF PATIENTS

9.1. Investigational Product Treatment Regimen

The term investigational product refers to either OCA (provided as part of this clinical study) or placebo.

Two treatment groups will be evaluated: OCA and placebo. Investigational product will be administered orally. Each dose will be made up of 1 tablet (ie, one OCA 5 mg tablet or one OCA 10 mg tablet, or matching placebo).

Investigational product will be taken orally with water for the duration of the study. Patients will be instructed to begin dosing on Day 1 and are to take investigational product at approximately the same time on dosing days. Patients must be instructed to swallow the tablet whole; they must not chew, divide, or crush the tablet.

At each study visit where the dose of investigational product is administered at the site, all assessments, except for the post-dose collection of blood samples for the PK assessment, must be completed before administration of investigational product.

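### The general adverse event tables compare crude patient incidence by arm with no stated data window and no person-time denominator, although blinded follow-up runs from 48 weeks to about 3 years

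*Protocol*

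**What the plan says.** Section numbers refer to Protocol Version 2. Section 6.1 makes safety and tolerability against placebo a primary objective. Section 15.4 says: "The incidence of TEAEs and SAEs will be tabulated by system organ class (SOC) and preferred term for each treatment group". Section 15.4.1 lists the tables, starting from "Patient incidence of TEAEs and the total number of entries by MedDRA SOC and PT" and continuing with severity, relationship, seriousness, and withdrawal of drug or from study. It adds: "Each AE summary will be displayed by treatment group". Section 9.1 fixes the number of groups: "Two treatment groups will be evaluated: OCA and placebo". The only further split is "This summary will be repeated for all subgroups", and the subgroups are not named.

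On time, Section 7.1.3 says: "Patients will receive double-blind treatment for at least 48 weeks". It then continues blinded treatment until everyone has completed the 48-week "treatment period and the database for that period is locked (approximately 3 years"). Adverse events are collected until participation ends (13.1.4.1), and the TEAE definition has no end point (13.1.1.3).

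Section 15.4.3 defines event days per patient-year and Kaplan-Meier analyses for pruritus and fatigue. Section 15.6 gives Kaplan-Meier, stratified log-rank and Cox analyses for death, transplant, the MELD threshold, hospitalised decompensation events and uncontrolled ascites, and applies the same methods to hepatocellular carcinoma. The TEAE and SAE tables have no equivalent. Nor does drug-related hepatic injury, which is adjudicated under 15.9.

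**The concern.** A percentage of patients with an event has a clear meaning only over a stated period. Here planned blinded follow-up varies roughly threefold between patients and the tables do not say how much of it they cover. The same true event rate therefore gives very different percentages depending on a choice the protocol leaves open.

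The comparison between arms carries a separate risk. Crude incidence treats a patient seen for six months like one seen for three years. If more OCA than placebo patients die, are transplanted or withdraw early, OCA has less time in which to record events and its incidence is understated. If placebo patients leave earlier, the error runs the other way. Differential loss is plausible here. Section 5.4.4 expects a high rate of clinical events. Transplant ends the visit schedule (8.4.2), and consent may be withdrawn at any time (8.4). Liver chemistry elevations attributed to the product lead to its discontinuation (8.4.1.2). After that, continued visits are described as encouraged (8.4) or expected (8.4.3, 9.7.13), which does not guarantee them.

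**Working it through.** **The plan's own figures.** Section 15.4.1 states no number that can be reproduced. The group size follows from 15.2: 20 + 10 + 20 = 50, randomised 1:1, so about 25 per arm.

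**Step 1: how much the window matters.** The documents give no adverse event rate, so one is assumed. At a constant rate of 0.3 per patient-year, incidence is 1 − exp(−0.3 × 0.92) = 24% at 48 weeks (0.92 year) and 1 − exp(−0.3 × 3) = 59% at 3 years.

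**Step 2: effect on the arm comparison.**

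Inputs from the protocol: minimum blinded follow-up 0.92 year, maximum about 3 years.

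Assumptions: administrative follow-up uniform between those limits; a fraction d leaves follow-up at 0.5 year; constant event rate h of 0.2, 0.3 or 0.5 per year. The only related figure in the documents is a 15% discontinuation rate for the OCA group (15.2). It is not split by arm and does not describe loss from follow-up.

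- Full blinded period: incidence = (1 − d) × A(h) + d × [1 − exp(−0.5h)], where A(h) is the mean of 1 − exp(−ht) over t uniform from 0.92 to 3.
- Week 48 cut: the same, with A(h) replaced by 1 − exp(−0.92h).

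Worked case, h = 0.3 in both arms, d = 0.30 on OCA and 0.10 on placebo. A = 0.4355, the Week 48 value is 0.2412 and the early-exit value is 0.1393.

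- Full period: OCA 0.7 × 0.4355 + 0.3 × 0.1393 = 0.347; placebo 0.9 × 0.4355 + 0.1 × 0.1393 = 0.406; ratio 0.85.
- Week 48: OCA 0.7 × 0.2412 + 0.3 × 0.1393 = 0.211; placebo 0.9 × 0.2412 + 0.1 × 0.1393 = 0.231; ratio 0.91.

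Relative risk shown when the true rates are equal, over h = 0.2 to 0.5:

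| Early exit, OCA vs placebo | Full blinded period | Week 48 cut |
|---|---|---|
| Equal | 1.00 | 1.00 |
| 20% vs 10% | 0.92–0.93 | 0.95–0.96 |
| 30% vs 10% | 0.85–0.86 | 0.91–0.92 |
| 10% vs 20% | 1.07–1.08 | 1.04–1.05 |
| 10% vs 30% | 1.16–1.18 | 1.09–1.10 |

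**Step 3: cross-check with another dropout model.** Take continuous exponential loss of 30% on OCA and 15% on placebo by Week 48, so that incidence over follow-up c is r/(r + λ) × [1 − exp(−(r + λ)c)], with r the event rate and λ the loss rate. With equal true rates, full-period incidence is 31.3% vs 37.2% at 0.3 per year, 45.0% vs 52.6% at 0.5 and 65.5% vs 74.2% at 1.0. OCA looks better by 6 to 9 percentage points. With a Week 48 cut the gap is 2 to 4 points. Direction and ordering agree with Step 2.

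**The case against.** **Table detail belongs in the SAP.** Exposure-adjusted rates and reporting windows are often left there, and the SAP is not shown. This limits the weight of the point. It does not remove it, because the protocol itself names the summary measure for a primary objective and does define patient-years and Kaplan-Meier methods at protocol level for two symptoms.

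**Randomisation balances follow-up.** This stands for administrative follow-up. Stopping drug is also not the same as leaving the study. Bias needs differential loss, which the documents neither predict nor exclude.

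**The main hepatic outcomes are already covered.** Largely true: 15.6 analyses them as time to event, and laboratory values are summarised by visit (15.4.2). The gap is the general TEAE and SAE tables and adjudicated drug-related hepatic injury.

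**Stronger readings a reader might infer.**

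- *The tables span 3 years.* The protocol does not say so. The 48-week period has its own database lock and 15.5 calls Week 48 the end of the study, so a Week 48 cut is possible. The defect is that the window is unstated.
- *A real excess would be hidden.* A true 30% higher OCA rate appears as 1.01–1.05 only with both a 30% vs 10% exit split and the full window. It appears as 1.08–1.14 at 20% vs 10%, and as 1.13–1.15 at 30% vs 10% with a Week 48 cut. Even with equal 15% loss it appears as 1.16–1.23 over the full period, because cumulative proportions saturate; that part is not follow-up bias.
- *Placebo at the same sham titration step is a matched comparator for dose.* It is not. Up-titration depends on tolerability, laboratory results and Child-Pugh class (7.3, 7.4), so patients reaching a step are selected differently in each arm.
- *Any dose relation is lost.* Too strong. Section 6.3 sets PK against safety and tolerability as an objective.

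**Conclusion.** The point holds as a moderate weakness that is cheap to repair. Section 15.4.1 fixes crude incidence by arm, with no window and no person-time, for a primary objective under widely varying follow-up. The distortion is zero with equal loss. With 20–30% early exit on OCA against 10% on placebo it is a relative risk of about 0.85–0.93 over the full blinded period, or 0.91–0.96 to Week 48, when the true rates are equal. These sizes rest on assumed exit fractions, exit at half a year, uniform administrative follow-up and constant event rates; none comes from the protocol. The finding that needs no dropout assumption is that a percentage without a window cannot be interpreted when planned follow-up ranges from 48 weeks to about 3 years.

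**What to change.** In Section 15.4.1:

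1. State the data window. Present TEAEs, SAEs and adjudicated drug-related hepatic injury for Day 1 to Week 48 and for the full blinded period.
2. Beside the crude incidence, give the exposure-adjusted incidence rate by arm: patients with a first event divided by patient-years at risk. Add a 95% CI for the OCA minus placebo difference. Define time at risk, including whether time after stopping drug counts.
3. If adverse events are shown by dose regimen at onset, give person-time per regimen, label the display descriptive and make no treatment contrast by step.

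No new data or visits are needed. The costs are additional tables and sparse counts with about 25 patients per arm. First-event rates assume a roughly constant hazard, which titration may violate, and adjusting for person-time does not remove bias if patients leave because of their prognosis. The fixed Week 48 table should therefore stand beside the rates.
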